⁸ <https://www.cdc.gov/nccdphp/dnpao/growthcharts/resources/sas-who.htm> following WHO's method

⁹ Abdel-Rahman, Susan M et al. "Construction of Lambda, Mu, Sigma Values for Determining Mid-Upper Arm Circumference z Scores in U.S. Children Aged 2 Months Through 18 Years." *Nutrition in clinical practice* : official publication of the American Society for Parenteral and Enteral Nutrition vol. 32,1 (2017): 68-76.

The number and percent of patients achieving positive pruritus assessment for more than 50% of the time will be summarised by treatment group. Both AM and PM pruritus assessments will be included in the analysis of this endpoint. A cumulative distribution function (CDF) plot showing proportions of patients achieving positive pruritus assessment for more than X% of the time, X is the time of achieving positive pruritus assessment from 0 to 100%, by treatment group will be provided.

❖ Proportion of Responders for Pruritus Scores

The proportion of responders for pruritus scores will be tabulated by visit based on monthly scores and bi-weekly scores. The 95% CI of the proportion of responders will be provided, based on the exact method of Clopper-Pearson. A responder is defined as a patient who reports a decrease in pruritus score from unrounded baseline equivalent to or greater than the threshold of meaningful change estimated from the blinded psychometric analysis; the results of the blinded psychometric analysis across all anchors support a threshold of 1.0 point for AM, PM and AM and PM scratching scores. Baseline 1 and 2, defined in the table of derived variables in [Appendix A](#), will be used for data analysis. Baseline 1 will only be used for patients in Cohort 1 who were on odevixibat in Study A4250-005.

❖ Biliary Diversion Surgery and Liver Transplantation

Number and percent of patients undergoing biliary diversion surgery and/or liver transplantation will be summarised by using descriptive statistics. A 95% CI also will be presented for the corresponding percentage. These parameters will be evaluated separately and together at Weeks 24, 48, 72 and all visits (every 16 weeks) during the optional extension period.

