AM & PM baseline, daily, weekly, and monthly score (scratching, itch severity)	
For both the Albireo ObsRO scratching item and the Albireo PRO itch severity score:
 
A daily AM & PM score will be averaged from the 2 ratings for each day. A daily score will be considered missing if both assessments are missing.
 
A weekly score will be calculated by averaging all non-missing AM and PM scores in a week. A weekly score will be considered missing if ≥ 8 out of 14 assessments in a week are missing.
 
A monthly score will be calculated by averaging all non-missing AM and PM scores in a month (28 days). A monthly score will be considered missing if ≥ 29 out of 56 assessments in a month are missing.
 
An average score of AM & PM at each visit after Week 24 will be calculated by averaging all non-missing AM and PM scores between 2 visits with analysis windows applied (Appendix B). 50% rule is applied based on the number of planned assessments.
 
All non-missing AM scores from the period of 14 days before or on the first dose day of study medications, and all non-missing PM scores from the period of 14 days before the first dose day of study medications will be averaged as the AM & PM baseline score. Baseline score will be considered missing if ≥ 15 out of 28 assessments in the 14 days are missing. Rounded baseline score will be used for the analysis.
 
One thing of note:
 
Inclusion criteria No. 4 in Study A4250-005:
 
Cohort 1: Patient must have history of significant pruritus and a caregiver-reported observed scratching in the eDiary average of ≥ 2 (on 0 to 4 scale) in the 2 weeks prior to randomisation in Study A4250-005.
 
Inclusion criteria No. 4 in Study A4250-008:
 
Cohort 2: Patient must have history of significant pruritus and a caregiver-reported observed scratching or patient reported itching (for patients > 18 with no caregiver-reported observed scratching) in the eDiary average of ≥ 2 (on 0 to 4 scale) in the 2 weeks prior to the screening/inclusion visit (Visit 1) in Study A4250-008.
 
The pruritus score for purposes of establishing eligibility was calculated by taking the average of the worse of the two scores for each day. The values for week one were averaged and the values for week 2 were averaged. The two weekly averages were then averaged to provide a single score. If this score was ≥ 2 the pruritus eligibility requirement was met. The calculation of pruritus eligibility score is different from the calculation of the baseline pruritus score defined in the SAP.

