
VARIABLES	FORMULA
Average of change from baseline from each AM and PM scores (scratching, itch severity)	
The calculation below is based on the change from baseline in each AM and PM score. The values based on this calculation will be used for data analysis.
 
Change from baseline (daily) will be calculated by averaging all non-missing values of change from baseline (AM and PM) in a day. A daily change from baseline will be considered missing if both AM and PM change from baseline in a day are missing.
 
Change from baseline (weekly) will be calculated by averaging all non-missing values of change from baseline (AM and PM) in a week. A weekly change from baseline will be considered missing if ≥ 8 out of 14 change from baseline values in a week are missing.
 
Change from baseline (monthly) will be calculated by averaging all non-missing values of change from baseline (AM and PM) in a month (28 days). A monthly change from baseline will be considered missing if ≥ 29 out of 56 assessments in a month are missing.
 
Change from baseline at each visit after Week 24 will be calculated by averaging all non-missing values of change from baseline (AM and PM) between 2 visits with analysis windows applied (Appendix B). 50% rule is applied based on the number of planned assessments.

Baseline, daily, weekly, and monthly (sleep parameters, such as difficulty falling asleep and staying asleep, tiredness, the number of awakenings)	For patient- and observer-reported outcome scores of sleep parameters, the same approach above will be used as for scratching/itch severity by AM and PM, respectively, since there is just one rating per day.
Proportion of positive pruritus assessments	No imputation will be made for any missing data. The assessments after intercurrent events (premature treatment discontinuation, death, or initiation of rescue treatments such as biliary diversion surgery or liver transplantation) will be treated as missing and excluded from analysis. The proportion of positive pruritus assessments will be calculated based on reported eDiary data only. 50% rule will be applied based on the number of planned assessments (Appendix B).

VARIABLES	FORMULA

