Baseline for proportion of responders for pruritus scores	
Baseline 1 is defined as the average of all non-missing daily scores from 14 days prior to the first dose of study drug in study A4250-005.
 
Baseline 2 is defined as the average of all non-missing daily scores from 14 days prior to the first dose of study drug in study A4250-008 (For patients in Cohort 1, the pre-dose assessments of Study A4250-008 can be from Study A4250-005).
 
Baseline score will be considered missing if ≥ 8 out of 14 assessments in the 14 days are missing. The unrounded baseline score will be used for the analysis.

Derivations for Safety Parameters	
AE duration (days)	AE end date–AE start date + 1
TEAEs	An AE (classified by preferred term) occurring during the treatment period and within 28 days follow-up after the last dose that a) has a start date on or after the first dose date of study drug, or b) has a start date before the date of the first dose date of study drug, but worsened in severity on or after the date of the first dose date of study drug. If an AE started in Study A4250-005 and was ongoing at the time of enrolment in Study A4250-008, the AE will not be considered a TEAE unless it worsens in severity on or after the date of the first dose date of study drug.

AE: adverse event; BMI: body mass index; CRF: case report form; eDiary: electronic diary; ObsRO: observer-reported outcome; PFIC: progressive familial intrahepatic cholestasis; PRO: patient-reported outcome; SAP: statistical analysis plan; TEAEs: treatment-emergent adverse events

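### The combined AM and PM pruritus responder uses a single baseline with a looser completeness rule and no clear AM/PM matching, so a change in diary mix can misclassify patients near the 1.0-point cut

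*SAP*

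**What the plan says.** SAP Section 9.6.4 adds a responder analysis to the secondary endpoints: "The proportion of responders for pruritus scores will be tabulated by visit based on monthly scores and bi-weekly scores". A responder is a patient with "a decrease in pruritus score from unrounded baseline equivalent to or greater than the threshold of meaningful change", and the psychometric results are said to "support a threshold of 1.0 point for AM, PM and AM and PM scratching scores". The section sends the reader to Appendix A for the baselines.

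Appendix A, Table 3 then contains four relevant rows:

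- **Responder baseline.** A single value, "the average of all non-missing daily scores from 14 days prior to the first dose of study drug in study A4250-008" (Baseline 1 is built the same way on Study A4250-005). It is missing when 8 or more of 14 assessments are missing, and it is used unrounded.
- **General AM & PM scores.** For the daily score, "A daily score will be considered missing if both assessments are missing". The monthly score averages the individual AM and PM ratings and is missing when 29 or more of 56 are missing. The general AM & PM baseline is missing when 15 or more "out of 28 assessments in the 14 days are missing. Rounded baseline score will be used for the analysis".
- **Separate AM and PM scores.** Each baseline has 14 planned ratings and is missing when 8 or more are missing.
- **Average change.** "The calculation below is based on the change from baseline in each AM and PM score". AM and PM changes are pooled, and the row says that the resulting values are for use in the data analysis.

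Sections 4.1 and 9.6.3 also compare AM scores with an AM baseline and PM scores with a PM baseline for the positive-assessment endpoint.

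**The concern.** AM ratings describe the night and PM ratings the day (Section 3.3.2), and a patient's level may differ between them. Where the SAP compares like with like, it does not matter which diary was completed. The combined responder appears to drop that safeguard. It subtracts a mixed follow-up score from one mixed baseline, and nothing fixes the mix at either end. It also accepts a thinner baseline than the general AM & PM row does.

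If the mix of entries changes between baseline and follow-up, the score moves although the pruritus has not. At a sharp cut, that can turn a non-responder into a responder or the reverse. The responder table and the mean-change table can then treat the same patient differently. Monitoring would not reliably catch the pattern: under Section 3.1 the reminder call is triggered only when both entries of a day are missing.

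**Working it through.** The SAP gives no figure for the effect of diary mix, so there is none to reproduce. Its rules can be worked through.

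**1. Completeness (Table 3)**

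- Responder baseline: at most 7 of 14 may be missing, so 14 − 7 = 7 daily scores are enough. With one rating per day that is 7 × 1 = 7 of 28 ratings, or 25%.
- General AM & PM baseline: 28 − 14 = 14 of 28 ratings, or 50%.
- Monthly score: 56 − 28 = 28 of 56 ratings. A full month of one side alone is exactly 28, so it passes.

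**2. Effect of the mix**

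Hold a patient's AM level a and PM level p constant, so the true change is 0. Let g = a − p, and let s_B and s_F be the AM shares of the baseline and follow-up averages. Then

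apparent drop = (s_B − s_F) × g.

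- One time point one-sided: s_B − s_F = 1 − 0.5 = 0.5, a shift of g/2. A drop of 1.0 needs g = 1.0/0.5 = 2.0.
- Complete switch: s_B − s_F = 1 − 0 = 1, a shift of g. A drop of 1.0 needs g = 1.0.

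| AM / PM level | AM-only baseline, full follow-up | AM-only baseline, PM-only follow-up |
|---|---|---|
| 3 / 1 | 3 − 2 = 1.0 | 3 − 1 = 2.0 |
| 3 / 2 | 3 − 2.5 = 0.5 | 3 − 2 = 1.0 |
| 2.5 / 2 | 2.5 − 2.25 = 0.25 | 2.5 − 2 = 0.5 |

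Smaller gaps matter only near the cut. With a true drop of 0.75 and g = 0.5, an AM-only baseline and full follow-up give 0.75 + 0.25 = 1.0, a responder. The opposite pattern hides true responders.

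**3. Days against ratings**

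The responder baseline averages days and the monthly score averages ratings. Apply both to the same entries, with a share x of reported days having a single rating. Let u be the mean of those days and v the mean of the days with two ratings. The two averages differ by

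(u − v) × x(1 − x)/(2 − x).

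The factor peaks at 0.172, at x = 0.586. With constant levels and all single ratings on one side, u − v = g/2, so the difference is at most 0.086g, or about 0.04 point at g = 0.5. Even with u − v = 4, the whole scale, it is 4 × 0.172 = 0.69. With complete diaries it is 0.

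**4. Illustration near the cut (assumed values)**

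Assume g of 0.3 to 0.5 and a change distributed as N(−1.0, SD 1.0), centred on the cut, where P(response) = 50%.

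- One time point one-sided: shift 0.15 to 0.25, so the probability becomes 56–60%, or 44–40% in the other direction.
- Complete switch: shift 0.30 to 0.50, so 62–69%, or 38–31%.

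This is the most sensitive position. If 5% of patients (assumed) were one-sided at one time point, all in the same direction, the overall rate would move by 0.05 × 6 to 10 points = 0.3 to 0.5 point.

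**5. Table 3's matched change, same patients**

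AM change against the AM baseline is 0, PM change against the PM baseline is 0, and the pooled change is 0. A patient with an AM-only baseline and PM-only follow-up has no evaluable change. Under the responder row, the same patient is classified.

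**The case against.** **The average-change row may already govern.** It says its values are for data analysis, and if it applied to responders the problem would go. This stands in part: the SAP does not exclude it. But Section 9.6.4 defines the responder on a score against an unrounded baseline, and Table 3 provides a single responder baseline that would have no role for the combined score if the matched change were used. What can be said is that the governing derivation is not clear.

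**The 7-of-28 figure rests on one reading.** The responder row counts 14 assessments, not days, and the separate AM and PM row uses the same count for 14 planned ratings. The reference to daily scores favours counting days for the combined score, but the text is ambiguous. If the rule was meant for AM or PM alone, the responder row sets no completeness rule for its combined baseline.

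**The follow-up rule is not fully described by 28 of 56.** Appendix B Tables 8 and 9 set the responder intervals and state the 50% rule in expected diary days, and some Table 8 intervals expect 21 days. The bi-weekly score has a window in Table 9 but no formula at the level of ratings. This is correct, and it does not remove the one-sided diary problem.

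**Two stronger readings are tempting and are not supported.** A reader might infer that patients will become responders through reporting pattern alone. That needs a gap of at least 1.0 with a complete switch, or 2.0 with one one-sided time point; the SAP gives no gap, and one of 0.3 to 0.5 cannot do it. A reader might also blame the averaging of days against ratings. Step 3 shows that this is minor and cannot reach 1.0 by itself.

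**The stakes are low.** The endpoint is secondary and descriptive, and Section 5 states that there is no formal hypothesis testing. AM-only and PM-only responder rates are not affected. All of this stands.

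**Conclusion.** The point holds as a gap in definition with a limited effect. For the combined AM and PM responder, the baseline can on the natural reading pass with half the ratings required elsewhere in Table 3. No AM/PM balance is required at baseline or follow-up, and the SAP's own matching is not clearly applied.

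The consequence is possible misclassification of patients near 1.0 point, by a shift of up to half the AM-PM gap or, after a complete switch, the whole gap. The frequency cannot be stated, because the SAP gives neither the gap nor the number of one-sided reporters. The percentages in step 4 rest on an assumed gap, SD and centring and only show sensitivity at the cut. The Clopper-Pearson interval around the responder rate does not reflect this misclassification. No test depends on it, so it is a low-priority correction.

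**What to change.** State in Section 9.6.4 and in the responder row of Table 3 that:

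- the combined responder has a change of −1.0 or lower, using Table 3's average change: all non-missing AM and PM changes, each against its own AM or PM baseline, pooled over the Table 8 or Table 9 interval, with unrounded baselines;
- the 8-of-14 rule for the combined score is replaced by the separate AM and PM rule, so that at least 7 of 14 AM and 7 of 14 PM ratings are needed at baseline;
- AM-only and PM-only responders use the AM or the PM baseline respectively;
- the bi-weekly score is defined in the same way.

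The pooled change should be named explicitly. A simple mean of the AM change and the PM change is a different quantity when the AM and PM counts are unequal, which is the case at issue.

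The cost is SAP wording and a small programming change. A few patients with one-sided diaries become non-evaluable for the combined rate but remain in the AM or PM rate. A one-sided follow-up that still passes will reflect only that side's change, but the AM-PM difference in level no longer enters.

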Appendix B: Visit Window

The observation closest to the target day is the measurement used in the analysis for each visit. The following visit window will apply for all laboratory parameters, questionnaires, vital signs, physical measurements and other efficacy parameters in the study, if not otherwise specified.

Table 4: Analysis Visit Window (General)

TIMING OF ASSESSMENT (DAYS RELATIVE TO TREATMENT)	VISIT NAME TO DISPLAY FOR ANALYSIS	TARGET DAY	STUDY DAY (RELATIVE DAY)
Screening (Days -56 to -1)	Baseline		≤ -1
Day 1 Week 1	Baseline		1 (Pre-dose)
Week 4 (± 5 days)	Week 4	28	Post-baseline - 56
Week 12 (± 7 days)	Week 12	84	57–119
Week 22 (± 7 days)	Week 22	154	120–161
Week 24 (± 7 days)	Week 24	168	162–210
Week 36 (± 7 days)	Week 36	252	211–287
Week 46 (± 7 days)	Week 46	322	288–329
Week 48 (± 7 days)	Week 48	336	330–378
Week 60 (± 7 days)	Week 60	420	379–455
Week 70 (± 7 days)	Week 70	490	456–497
Week 72/EOT (± 7 days)	Week 72	504	498–(Last dose day + 14)
4 weeks post last dose of study drug (± 7 days)	Follow-up	28 post last dose	Last dose day + 15–Last dose day + 28
For patients who enter optional extension period:			
Week 72/EOT (± 7 days)	Week 72	504	498– Min(518, start day of optional extension period -1)
Week 88	Week 88	616	Min(519, start day of optional extension period)–672
Week 104, 120, ... (continue every 16 weeks)	Week 104, 120, ... (continue every 16 weeks)	7*week #	(7*(week # - 8) + 1) – Min(7*(week # + 8), Last dose day + 14)

Table 5: Analysis Visit Windows for GIC/GIS, Physical Measurements and Selected Lab Test)

TIMING OF ASSESSMENT (DAYS RELATIVE TO TREATMENT)	VISIT NAME TO DISPLAY FOR ANALYSIS	TARGET DAY	STUDY DAY (RELATIVE DAY)
Screening (Days -56 to -1)	Baseline		≤ -1
Day 1 Week 1	Baseline		1 (Pre-dose)
Week 4 (± 5 days)	Week 4	28	Post-baseline - 56
Week 12 (± 7 days)	Week 12	84	57–126
Week 24 (± 7 days)	Week 24	168	127–252
Week 48 (± 7 days)	Week 48	336	253–420
Week 72/EOT (± 7 days)	Week 72	504	421–(Last dose day + 14)
4 weeks post last dose of study drug (± 7 days)	Follow-up	28 post last dose	Last dose day + 15–Last dose day + 28
For patients who enter optional extension period:			
Week 72/EOT (± 7 days)	Week 72	504	421– Min(518, start day of optional extension period -1)
Week 88	Week 88	616	Min(519, start day of optional extension period)–672
Week 104, 120, ... (continue every 16 weeks)	Week 104, 120, ... (continue every 16 weeks)	7*week #	(7*(week # - 8) + 1) – Min(7*(week # + 8), Last dose day + 14)

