9.7 Safety Analyses

All definitions relative to safety endpoints are detailed in [Section 4.4](#).

All the safety analyses will be performed on the FAS for all safety variables specified below and summarised by cohort/treatment subgroup and overall.

For each safety variable, the last value collected before the first dose of study drug will be used as baseline (i.e., Baseline 2 defined in the table of derived variables in [Appendix A](#)) for all analyses unless otherwise specified.

In addition, different with efficacy analysis, laboratory related safety endpoints will be considered up to 28 days follow-up after the last dose.

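### Fixed visit windows before Week 72 (and at Week 88) overlap the Follow-up window for early discontinuers, with no precedence rule, so an off-drug safety value can be summarised under a scheduled week

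*SAP*

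**What the plan says.** SAP Appendix B governs safety as well as efficacy data: "The following visit window will apply for all laboratory parameters, questionnaires, vital signs, physical measurements and other efficacy parameters in the study". Its selection rule is "The observation closest to the target day is the measurement used in the analysis for each visit". The only additions, given after Table 6, are that the earlier value wins a tie and that central laboratory results are preferred to local ones.

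Tables 4 to 6 treat the end of dosing unevenly:

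- Rows before Week 72 are fixed day ranges. In Table 4, Week 36 is Days 211 to 287 with target Day 252.
- Week 72 for patients not entering the extension is capped; in Table 4 it reads "498–(Last dose day + 14".
- Week 88 has a fixed end: "Min(519, start day of optional extension period)–672".
- Week 104 and later are capped: "Min(7*(week # + 8), Last dose day + 14".
- Follow-up runs "Last dose day + 15–Last dose day + 28", although the visit itself is allowed "4 weeks post last dose of study drug (± 7 days", that is, last dose + 21 to + 35.

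Section 3.1 gives prematurely withdrawn patients the Visit 11 assessments at withdrawal and a follow-up visit 28 days after the last dose. Section 9.7 keeps post-treatment safety data: "laboratory related safety endpoints will be considered up to 28 days follow-up after the last dose". The cut at 14 days in Section 9.6 and the exclusion from last dose + 15 in Section 8.1.1 apply to efficacy.

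**The concern.** For a patient who stops before Week 72, the follow-up visit usually lies inside both the Follow-up row and a fixed scheduled row. The plan does not say which row takes precedence, or that a value may be used only once. Closeness to target then decides, without regard to whether the patient was still on drug.

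Two things can follow. A patient can gain a value for a week reached only after dosing stopped. Or an off-drug value can displace the end-of-treatment value in the same window.

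The outputs exposed are the by-visit laboratory summaries and mean-change figures (Section 9.7.2), vital signs (Section 9.7.3) and physical examinations (Section 9.7.4). Groups may be small: Section 9.7.2 drops a group from a figure when fewer than 5 patients have data. A few misplaced values could move a mean.

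**Working it through.** The plan gives no figure to reproduce. The check applies its window rules to every possible last-dose day.

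**Inputs.** Windows and targets are from Table 4, with the Week 4 window taken to start on Day 2. Let L be the last-dose day, 1 to 503. Assume the end-of-treatment visit is on Day L, the follow-up visit on Day L + 28, and earlier scheduled visits on their target days.

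**Rules.** For a window from a to b with target t:

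- Overlap: a ≤ L + 28 ≤ b.
- Follow-up is the only value in the window: overlap and L < a.
- Follow-up displaces the end-of-treatment value: overlap, L ≥ a and |L + 28 − t| < |L − t|. The last condition reduces to L < t − 14.

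**Week 36 in full** (a = 211, b = 287, t = 252). Overlap is L = 183 to 259, or 77 days. Follow-up is the only value for L = 183 to 210, or 28 days. It displaces for L = 211 to 237 (because L < 238), or 27 days. It is selected on 28 + 27 = 55 days.

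**All Table 4 rows before Week 72:**

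| Row | Overlap | Only value | Displaces | Selected |
|---|---|---|---|---|
| Week 4 | 28 | 1 | 12 | 13 |
| Week 12 | 63 | 28 | 13 | 41 |
| Week 22 | 42 | 28 | 14 | 42 |
| Week 24 | 49 | 28 | 0 | 28 |
| Week 36 | 77 | 28 | 27 | 55 |
| Week 46 | 42 | 28 | 14 | 42 |
| Week 48 | 49 | 28 | 0 | 28 |
| Week 60 | 77 | 28 | 27 | 55 |
| Week 70 | 42 | 28 | 14 | 42 |
| Total | 469 | 225 | 121 | 346 |

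Selected: 346/503 = 69%. Displacing: 121/503 = 24%. For L = 470 or later, L + 28 is at least 498, which is past the Week 70 row, so there is no overlap.

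**Examples.**

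- L = 225: end of treatment on Day 225, follow-up on Day 253. Distances from Day 252 are 27 and 1, so Week 36 takes the off-drug value. Day 253 also lies in Follow-up (Days 240 to 253).
- L = 190: follow-up on Day 218 becomes a Week 36 value although dosing stopped four weeks earlier. Nothing is displaced, because Day 190 lies in the Week 24 window.
- L = 245: follow-up on Day 273 is 21 days from target and end of treatment is 7, so the on-drug value is kept.

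**Sensitivity to visit timing.** On last-dose Days 8 to 469, the follow-up value is selected on 339 of 462 days (73%) with the visit at + 28 and on 313 of 462 (68%) at + 21.

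**Visit tolerance.** The allowance covers 15 days (+ 21 to + 35). Eight of them (+ 21 to + 28) are inside the Follow-up row and seven (+ 29 to + 35) are outside it. Laboratory values on those seven days are already excluded by Section 9.7. Vital signs and examinations have no such limit and can only go to a scheduled week.

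**Tables 5 and 6**, for assessments repeated at follow-up: overlap on 392 and 350 of 503 days, follow-up selected on 206 (41%) and 208 (41%).

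**Week 88**, if a follow-up visit takes place and the extension starts on Day 505: overlap for L = 505 to 644 (140 days). The value is selected when L < 616 − 14 = 602, that is, L = 505 to 601 (97 days).

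**The case against.** The strongest reply is that a Follow-up row keyed to last dose already exists, so a sensible programmer would give it priority. That may happen, but nothing written requires it, and the stated closest-to-target rule points the other way.

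A reader might infer that off-drug values will be reported as on-treatment values. The SAP does not support that: it labels values by week, does not call these summaries on-treatment, and deliberately keeps safety laboratory data for 28 days. What it supports is an overlap that the plan leaves unresolved.

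A reader might also infer that the last on-drug liver value is replaced in most early discontinuers. The larger count does not show this. On 225 of the 346 days nothing is replaced, and the number and timing of discontinuations are not given.

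Other limits stand:

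- Section 3.1 says the follow-up period does not occur for patients who continue into the extension, yet gives all prematurely withdrawn patients the 28-day visit. Week 88 is therefore conditional.
- Sections 3.3.4, 3.3.6, 3.3.8 and 3.3.11 do not list p-C4, autotaxin, PedsQL, Fibroscan or GIC/GIS at Visit 12, so much of Tables 5 and 6 may not be exposed.
- Highest/lowest shift tables, the eDISH plots (peak values) and the liver-monitoring listing (criterion-based) do not depend on visit assignment. Efficacy is protected by Sections 8.1.1 and 9.6.

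**Conclusion.** The point holds as an unresolved overlap in the rules for by-visit safety summaries. Under the literal rule and the visit timing assumed above, the follow-up value falls in a scheduled Table 4 row on 469 of 503 possible last-dose days and is selected there on 346. The share of patients affected, and the direction and size of any shift in a mean, cannot be derived from the SAP. Week 88, and Tables 5 and 6, count only where the follow-up assessment is actually made. The correction is worth making because the sponsor already uses the needed cap in other rows of the same tables.

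**What to change.** 1. In Tables 4, 5 and 6, end every scheduled row before Week 72, and the Week 88 row, at Min(stated upper limit, last dose day + 14).
2. State that values after last dose day + 14 belong only to Follow-up.
3. For non-laboratory values, extend the Follow-up row to last dose + 35 to match the visit allowance. Without this, the cap would leave values at + 29 to + 35 in no window. Safety laboratory values stay limited to + 28 by Section 9.7.

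With the cap, a follow-up visit at L + 28 can never fall in a scheduled row, because L + 28 > L + 14. The overlaps drop from 469, 392 and 350 days to 0 in Tables 4, 5 and 6. Values up to 14 days after last dose stay in the scheduled week, as they already do at Week 72. The cost is a short edit to three tables, one added sentence and a small programming change, with no new data collection.
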